January 26, 2024

Title: Creatine Supplementation At Simulated Altitude

Project Personnel: [name]. Department of Kinesiology and Public Health [contact]; [name]

Purpose

Military personnel are frequently exposed to extreme environments, including high altitude and hypoxic conditions, which severely limit exercise capacity and performance. For example, over 775,000 soldiers have been deployed to Afghanistan since 2001, many of which have been exposed to potentially life-threatening elevations above 4000 meters (13,123 ft) in locations such as the Tora Bora mountains (1,2). Surprisingly, very few methods have been developed to mitigate the effects of hypoxia on exercise performance (3), despite the Department of Defense prioritizing this area of research.

Previous studies have shown that creatine supplementation increases exercise performance at sea-level (4,5). Our team showed a 4% improvement in exercise performance with creatine supplementation (vs. Placebo) (4). However, no published study has examined whether creatine supplementation increases performance at altitude. The purpose of this study is to determine the effects of creatine supplementation on exercise performance at simulatedaltitude.

Methods and Protocol

Subjects

Sixty healthy adults (30 men and 30 women) will be recruited and enrolled. Inclusion criteria includes: 1) 18-40 years old, 2) BMI 18.5-40.0 kg/m² 3) habitually active (>150 minutes per/wk of moderate-vigorous physical activity). Exclusion criteria includes: 1) pregnant or trying to become pregnant 2) recent use of creatine supplementation and 3) supplement allergies.

Subject Recruitment & Study location

Recruitment efforts will be focused on California Polytechnic State University and the surrounding area. Participants will be recruited via flyers hat will be posted in physical locations around campus and the San Luis Obispo, CA area. These flyers will also be distributed electronically via campus lists and classes, and appropriate social media outlets. The flyer contains a QR code that can be used to access a contact information survey and preliminary eligiblity (See eligiblity script). If the participant is deemed eligible for the study, they will be asked to schedule a Zoom or in-person meeting with a member of the research staff to go over the study protocol in more detail and address any questions or concerns the participant may have.

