If the participant is interested in taking part in the study, they will be provided with an informed consent form (electronic via Adobe Sign or paper copy). Subjects will give both verbal and written informed consent. Similar to our previous studies, subjects may sign the informed consent with ink signature or via electronic signature using RedCap. RedCap is a secure web application for building and managing online surveys and databases. All testing and procedures will occur in the Human Performance Laboratory in the Kinesiology building (43A) at California Polytechnic State University.

Preliminary testing

Body weight via digital scale and height via stadiometer will be obtained. Subjects will also complete a physical activity questionnaire, health history questionnaire, and demographics questionnaire. Subjects will then complete a familiarization exercise performance test (repeated sprint test). Previous studies have shown a learning curve with the repeated sprint test (subjects get better at the test), and therefore will complete a familiarization test. The repeated sprint test involves six, 10-second sprints on a cycle ergometer (Racer-Mate Inc, Seattle, WA, USA) with 60 second recovery between each sprint [6]. Following a brief self-selected warm-up, the subject will build to their maximal cadence and then pedal maximally against a resistance of 0.075 kg/kg body weight for 10 seconds, followed by 60-seconds of recovery. The test will take approximately 10-15 minutes total time. We have previously used a similar protocol after creatine supplementation at sea-level (4), and the test is a validated measure of high-intensity exercise performance that mimics many physiological demands of military performance (6-8). Outcomes measures are peak power (watts), relative peak power (watts per kilogram), and fatigue index (watts per second).

Baseline Testing

At least 24 hours after the familiarization repeated sprint test, subjects will then return to the laboratory after an overnight fast. Subjects will complete a baseline Acute Mountain Sickness score (Lake Louise AMS score). Participants will then complete a baseline repeated sprint test, as described above. During the test, oxygen saturation and pulse will be collected on the index finger using a non-invasive pulse oximeter (ZacVrate, Inc.).

Randomization and Supplementation

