After baseline testing, subjects will be randomized (by sex, age, ethnicity, and peak power), using a double-blinded parallel design, to placebo (calcium 500 mg) or creatine supplementation (20 grams) for 2 days. The supplements will be given to subjects in equal numbers of unidentifiable capsules. As we previusly described (4), each total daily dose will be divided into 4 capsules to reduce gastrointestional stress. Subjects will be instructed to take 4 capsules a day, several hours apart, for two days straight (4,9,12,13).

Simulated Altitude Testing After the 2 day supplementation treatment, subjects will arrive in the laboratory after an overnight fast and weight will be obtained. Subjects will rest for 30 minutes breathing a hypoxic gas mixture containing 12.8% oxygen, equivalent to 4000 meters elevation (13,123 feet elevation). The hypoxic gas will be emitted from a hypoxic generator (Hypoxico Hypoxic Generator, New York, NY) that lowers the oxygen content of room air and administers it to subjects through a HEPA filter and sealed facemask. This is a validated method commonly used to simulate altitude in research (10). Subjects will then complete the Acute Mountain Sickness score, and then perform the same repeated sprint test as described above. Oxygen saturation and pulse will be collected on the index finger using a non-invasive pulse oximeter (ZacVrate, Inc.).

After completion of the study, a researcher will go over the subjects' repeated exercise test results with them in person.

Description of Risks and Benefits

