General Risk of Exercise Despite the well-documented benefits, there are minimal risks associated with exercise (11). Participants may experience fatigue and muscle soreness due to an increase in physical activity from previous sedentary states. These health risks are small in people with no prior history of cardiovascular, respiratory, or musculoskeletal disease or injury. Any ordinary fatigue or muscle soreness is temporary and usually lasts 24-96 hours (about 4 days). With any exercise, there is a slightly increased risk of acute cardiovascular complications. The American College of Sports Medicine notes that although the relative risk of unfavorable outcomes slightly increases with exercise, the absolute risk of a cardiac event is still very low (1 per 133,000 men and 1 per 769,000 women). To ensure the safety of subjects during all exercise tests, we will follow American College of Sports Medicine guidelines. During the test, if the subject experiences any problems (light-headed, nauseous, excessive redness in the face, or heart palpitations) the exercise test will be immediately stopped. Additionally, we will be monitoring the participant's oxygen saturation and provide additional caution if their oxygen saturation levels drop below 80% (which is not expected). After the exercise test, subjects will cool-down for a 3-minute period or until heart rate reaches close to resting values. There will always be at least 2 CPR certified persons in the room during testing, one who can perform CPR and one who can call 911. The lead investigator and/or trained students have administered numerous exercise tests with no adverse events.

Supplementation Risks

Creatine supplementation has minimal side effects, espically short-term supplementation. There is a slight risk of acute water retention [7]. Creatine supplementation has been deemed safe in the dosages prescribed in this study in individuals free of gastrointestinal, metabolic, renal, liver, or cardiorespiratory diseases [8,9]. Individuals with these conditions will be screened and excluded from participation using the previously described screening methods.

Simulated-Altitude

There are minimal risk associated with simulated altitude for 45 minutes. Subjects may transiently feel lightheaded, dizzy, or fatigued, and may stop at any time.

Questionnaires

Subjects may omit any questions on the surveys (physical activity, health history, demographics, Acute Mountain Sickness score).

Benefits

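### The right to skip any health-history question undercuts the promised exclusion of people with five groups of disease

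*Protocol*

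**What the plan says.** The safety statement and the exclusion stand together in Description of Risks and Benefits, under Supplementation Risks: "Creatine supplementation has been deemed safe in the dosages prescribed in this study in individuals free of gastrointestinal, metabolic, renal, liver, or cardiorespiratory diseases". The next sentence reads: "Individuals with these conditions will be screened and excluded from participation using the previously described screening methods".

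The Questionnaires paragraph, a little further down, lets subjects leave out any item of four named surveys: physical activity, health history, demographics and the Acute Mountain Sickness score. It makes no exception for items that bear on eligibility or safety.

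The earlier text that the exclusion can point back to is as follows.

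- Subjects: "Sixty healthy adults (30 men and 30 women) will be recruited and enrolled". The numbered inclusions cover age, BMI and activity. Then: "Exclusion criteria includes: 1) pregnant or trying to become pregnant 2) recent use of creatine supplementation and 3) supplement allergies".
- Subject Recruitment & Study location: a QR code on the flyer lets a volunteer "access a contact information survey and preliminary eligiblity (See eligiblity script"). The script itself is not reproduced. "If the participant is deemed eligible for the study, they will be asked to schedule a Zoom or in-person meeting" with research staff.
- Preliminary testing: "Subjects will also complete a physical activity questionnaire, health history questionnaire, and demographics questionnaire". The familiarization sprint test comes next.

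**The concern.** The protocol makes a promise and, in the same section, grants a permission that works against it. An exclusion based on disease history works only if the history is obtained. If any item may be left blank and nothing says what follows from a blank, the questionnaire cannot by itself deliver the exclusion.

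What follows the questionnaire is demanding. Subjects sprint maximally at familiarization and again at baseline, take 20 g of creatine or placebo daily for two days, then breathe 12.8% oxygen for 30 minutes and sprint again. The safeguards under General Risk of Exercise (exercise-testing guidelines, stopping for symptoms, saturation monitoring, two CPR-certified persons) are stated for the exercise tests. On the capsule days, someone with renal, liver, metabolic or cardiorespiratory disease is protected, on the protocol's own account, by having been screened out beforehand.

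The stake is subject safety and a clear eligibility rule. The estimate of the creatine effect, the error rate and the sample size are not involved.

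**Working it through.** No formula applies. The check sets the statements side by side and counts.

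**1. Does the protocol state the exclusion?** Yes, under Supplementation Risks, for five groups: gastrointestinal, metabolic, renal, liver and cardiorespiratory disease.

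**2. Is it in the eligibility list?** The numbered exclusions in Subjects are three: pregnancy or trying to become pregnant, recent creatine use, and supplement allergies. Overlap with the five groups: 0 of 5. The inclusions (age, BMI, activity) name none of them either. The word healthy describes the population but is neither defined nor numbered.

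**3. Which screening methods does the exclusion refer back to?** Two candidates precede it.

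| Instrument | Where described | Content shown? | Items may be omitted? |
|---|---|---|---|
| Eligibility survey and script | Subject Recruitment & Study location | No | Not among the four surveys named |
| Health history questionnaire | Preliminary testing | Topic only | Yes, named expressly |

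Of the four surveys whose items may be omitted, 1 concerns health history and 0 is the eligibility survey.

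**4. Is a blank answer dealt with?** The protocol attaches no review step and no exclusion rule to the health history questionnaire, and does not say what happens when an item is skipped. In Preliminary testing the sprint test follows directly.

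**5. Can both rules be followed as written?** Take a volunteer with renal disease who skips that item. The omission rule is satisfied. The exclusion can be honoured only if staff learn of the disease another way, and the only other route described is the script whose content is not shown. If the script asks, the exclusion can still work. If it does not, this volunteer could reach the sprint test and the supplement without the promised screen. The document does not say which case applies.

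**6. Supplement exposure the screen is meant to cover.** Randomization and Supplementation: "Subjects will be instructed to take 4 capsules a day, several hours apart, for two days straight". 4 capsules per day × 2 days = 8 capsules.

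**The case against.** The strongest reply is that nothing here is a flat contradiction. The exclusion is stated outright, the list in Subjects is introduced in open-ended wording, and the subjects are called healthy. No sentence admits a person with one of the five diseases, and a reader who takes the protocol as a whole would exclude them. This stands as far as the list is concerned: its silence on the five groups is mainly a matter of placement. A reader might infer from that silence that the protocol permits their enrolment, but the documents do not support this.

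The second reply is that the eligibility script may already ask about these diseases, and that its survey is not among those whose items may be omitted. This also stands. A reader might infer that screening fails or that people with these diseases will be dosed. Neither is shown.

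Third, the omission sentence can be read as an ordinary statement that answers are voluntary. It does not say that a subject who skips a safety item is cleared. That is fair, but the permission covers every item, names health history, and has no stated consequence. Staff are left with a promise to exclude, a permission to withhold the information, and no rule joining them.

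Fourth, it would be too strong to call the exclusion the only precaution on the capsule days for all five groups. The daily dose is split into four capsules to limit gastrointestinal stress, which bears on one of them. The protocol does not offer that as protection for the other four.

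**Conclusion.** The point holds: the unrestricted right to omit health-history items undercuts the exclusion on which the protocol rests creatine safety, because that questionnaire is the only health-screening instrument whose subject matter the protocol describes. The absence of the five groups from the numbered exclusions (0 of 5) is a secondary matter of consistency.

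The size is limited. The number of the 60 planned subjects who might be affected cannot be estimated from the document, exposure is two days of supplement, and no harm or screening failure is demonstrated. No analysis or design figure changes. It should still be corrected, since it concerns subject safety and the correction is one of wording.

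The conclusion rests on the protocol text alone. If the eligibility script asks about all five groups and requires an answer, the practical gap largely closes and what remains is to say so in the protocol.

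**What to change.** 1. In the Questionnaires paragraph, limit the right to omit questions to items not used for eligibility or safety. State that a volunteer who leaves an eligibility or safety item blank is not cleared for the familiarization sprint test, the supplement or the hypoxic exposure. Answering remains voluntary; only clearance depends on it.
2. As a conforming edit, add a fourth exclusion in Subjects: gastrointestinal, metabolic, renal, liver or cardiorespiratory disease.
3. If the eligibility script already covers these diseases, name it under Supplementation Risks in place of the general reference to earlier screening methods.

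The cost is wording in the protocol and in any subject-facing text that repeats the right to omit questions. A few volunteers who decline these items would not be enrolled. No extra visit, test or staff is needed.

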There are no direct benefits for participating in this study, and subjects will not be compensated.

Data Collection

Statistics and Sample-size Calculation A repeated measures ANOVA will be used to determine differences on all variables of the repeated sprint test, adjusting for age, sex, ethnicity, and peak power A $\alpha < 0.05$ will be considered significant, and Tukey's HSD tests will be used to correct for multiple comparisons.

Data Storage, Sharing, and Destruction All data will be collected by trained student researchers under the authorization of the lead investigators. Data will be examined in a confidential fashion to preserve the privacy of each participant. All members of the research staff will have completed the required CITI and Cal Poly training modules. The data collected in this study will be accessible only to the researchers involved. All data will be stored on a password-protected computer and transferred to a password-protected cloud-based storage drive. All data will be de-identified using both a unique study and participant ID. The file linking the participant's identifiable information to their ID number and confidential data will be kept in a separate password-protected location. After 7 years following the completion of the study, hard copies of the data will be destroyed. Data specific to the aim of this study will be shared with scientific journals for publication purposes only, when appropriate.

Works Cited

- 5. Kreider RB. Effects of creatine supplementation on performance and training adaptations. *Mol Cell Biochem*. 2003;244(1):89-94. doi:10.1023/A:1022465203458
- 6. Bar-Or O. The Wingate anaerobic test an update on methodology, reliability and validity. *Sport Med.* 1987;4(6):381-394.

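### Relative peak power and fatigue index are not covariate-adjusted for their own collected baselines; own-baseline ANCOVA is a cheap improvement, modest in size if the repeated factor is visit

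*Protocol*

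**What the plan says.** The analysis is stated in the Protocol under Data Collection, Statistics and Sample-size Calculation. The planned model is a "repeated measures ANOVA will be used to determine differences on all variables of the repeated sprint test". Its covariates follow in one phrase: "adjusting for age, sex, ethnicity, and peak power". The repeated factor is not named, and no test occasion is attached to peak power.

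Preliminary testing defines three outcomes: "Outcomes measures are peak power (watts), relative peak power (watts per kilogram), and fatigue index (watts per second". The sprint test is done three times:

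- **Familiarization** (Preliminary testing): "Subjects will then complete a familiarization exercise performance test (repeated sprint test".
- **Baseline** (Baseline Testing): "Participants will then complete a baseline repeated sprint test, as described above".
- **Altitude** (Simulated Altitude Testing), where subjects "perform the same repeated sprint test as described above".

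Each test has several bouts: "The repeated sprint test involves six, 10-second sprints on a cycle ergometer". Under Randomization and Supplementation, "After baseline testing, subjects will be randomized (by sex, age, ethnicity, and peak power"). These are the same four variables as the covariate list.

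**The concern.** For the peak power outcome, the covariate list includes its own baseline, if the baseline-test value is meant. For relative peak power and fatigue index it does not: these two are adjusted for a different outcome. Yet the whole sprint test is run at baseline, so their own baselines will exist, and an outcome's own baseline is usually its strongest predictor.

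What is at stake is precision. The Purpose section asks one question, creatine against placebo at simulated altitude, and 60 subjects are to answer it. How much precision is left unused depends on the unnamed repeated factor. If it is visit, each outcome's own baseline already enters as the first repeated measure. If it is sprint 1 to 6 within the altitude test, the own baselines of these two outcomes are not used at all.

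**Working it through.** **Inputs.** From the Protocol: 60 subjects (Subjects) and alpha 0.05 (Statistics). It gives no SD, correlation, target effect in SD units, power or allocation ratio, so there is no stated figure to reproduce. Everything else is an assumption:

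- 30 per arm, two-sided test, true difference 0.5 SD, three ethnicity terms.
- ρ, the correlation of an outcome's altitude value with its own baseline given age, sex and ethnicity: 0.6, 0.7, 0.8, 0.9.
- r, the correlation of baseline peak power with that outcome's baseline: 0.3 to 0.6, and higher for relative peak power (see below).
- Peak power predicts nothing beyond the own baseline.

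**Residual variance, in units of the outcome variance**

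- Own-baseline ANCOVA: 1 − ρ²
- Visit reading, group-by-time (change from baseline): 2(1 − ρ)
- Visit reading with covariate-by-time terms: 2(1 − ρ) − ((1 − ρ)r)²
- Sprint reading, altitude values adjusted for peak power only: 1 − (ρr)²

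Before any cost in degrees of freedom, ANCOVA against plain change is (1 − ρ²) / (2(1 − ρ)) = (1 + ρ)/2.

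**Power.** The standard error is √(v × 2/30), where v is the residual variance, with a noncentral t on 58 − k degrees of freedom for k covariate terms. Own-baseline ANCOVA has k = 7 (own baseline, age, sex, three ethnicity terms, peak power). Without the own baseline, k = 6. The ranges run from chance covariate imbalance, which inflates the variance by 57/(57 − k), to full balance. Where r enters, they also cover r = 0.3 to 0.6.

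Example at ρ = 0.8 with full balance: ANCOVA v = 1 − 0.64 = 0.36, SE = √(0.36/15) = 0.155, power 0.886. Plain change v = 0.40, SE = √(0.40/15) = 0.163, power 0.853.

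| ρ | (1+ρ)/2 | Own-baseline ANCOVA | Visit, no covariate-by-time terms | Visit, with 6 such terms | Gain over visit (points) |
|---|---|---|---|---|---|
| 0.6 | 0.80 | 0.604–0.661 | 0.567 | 0.527–0.597 | +4 to +9 |
| 0.7 | 0.85 | 0.703–0.758 | 0.691 | 0.647–0.713 | +1 to +7 |
| 0.8 | 0.90 | 0.843–0.886 | 0.853 | 0.815–0.864 | −1 to +3 |
| 0.9 | 0.95 | 0.983–0.992 | 0.989 | 0.981–0.990 | −1 to 0 |

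Gains over the six-term model are taken at equal balance. The negative values arise only when ANCOVA with chance imbalance on seven terms is set against the covariate-free change analysis.

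**Sprint reading.** With r = 0.3 to 0.6, power is 0.447–0.531, 0.452–0.553, 0.457–0.582 and 0.463–0.617 for ρ = 0.6 to 0.9. For relative peak power, r may well be higher. Peak power is body weight times relative peak power. If these two are independent with CVs between 12% and 20% (assumed), r is about CV(relative) / √(CV(relative)² + CV(weight)²): 12/√(144 + 400) = 0.51 at one end, 0.71 at equal CVs, and 20/√(144 + 400) = 0.86 at the other. At ρ = 0.8 the sprint-reading power is then 0.589–0.637 for r = 0.71 and 0.698–0.745 for r = 0.86, against 0.843–0.886 with the own baseline. The shortfall is about 25 and 14 points; at r = 0.3 it is about 39.

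**Simulation check.** With 8,000 trials per cell and randomization stratified by sex only, group-by-time gave 0.56–0.57, 0.68–0.69, 0.86 and 0.99, and own-baseline ANCOVA gave 0.61, 0.70–0.71, 0.85 and 0.98–0.99. The mean estimate was 0.50 in every analysis, including the sprint reading, so none is biased.

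**Peak power outcome.** Once its own baseline is a covariate, change score and altitude value give the identical treatment estimate (0.0569 both ways in a numerical check).

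**The case against.** **It belongs in the SAP.** Only the Protocol is shown, and covariate details are commonly left to an SAP. That stands for mere silence. But the Protocol does not defer the matter: it names the model, the outcomes and a closed covariate list, and that stated choice can be improved.

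**On the natural reading little is lost.** A familiarization test because of a learning curve, then a baseline test, then the same test at altitude is a pre/post design, which points to visit as the repeated factor. This objection largely stands. It means that a reader may not infer from the covariate list alone that the own baselines go unused, or that the planned test is invalid. The larger loss belongs only to the sprint reading, which the text does not exclude but does not favour.

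**A reader might infer bias.** Since peak power carries no test occasion, one could suppose that the altitude value is the covariate, which would condition on a post-treatment measurement. The Protocol does not support this. The covariates are exactly the four randomization factors, and these are fixed after baseline testing and before any altitude test. What remains open is familiarization or baseline test. Both precede randomization, so neither biases the comparison.

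**Tukey's HSD would have nothing to correct** in a single two-arm contrast per outcome. This is right, and the fix has to say where that procedure still applies.

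**Conclusion.** The point holds as a minor, cheap improvement in precision. Two of the three outcomes lack their own baseline as a covariate although it is collected. On the visit reading, own-baseline ANCOVA has 0.80 to 0.95 of the variance of the change analysis before the cost in degrees of freedom. The power gain is 4 to 9 points at ρ = 0.6 and between about −1 and +3 at ρ = 0.8 to 0.9. On the sprint reading the loss is larger, and its size turns on the assumed r.

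No bias is shown on any reading that the Protocol supports. All sizes rest on assumed ρ, r, CVs, effect size and equal allocation, since the Protocol gives none of these. Confidence is medium.

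**What to change.** In Statistics and Sample-size Calculation, replace the ANOVA clause with wording such as:

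*For each of peak power, relative peak power and fatigue index, the altitude-test value will be compared between arms by ANCOVA adjusting for the same outcome's value at the baseline test, age, sex, ethnicity and baseline-test peak power (entered once for the peak power outcome). The creatine–placebo difference will be reported with its 95% CI. Any repeated measures analysis by visit or by sprint and arm is secondary, and Tukey's HSD applies only to pairwise comparisons within it.*

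This keeps all four randomization factors as covariates, ties peak power to the baseline test, and makes the main comparison independent of the unnamed repeated factor. It costs one clause and about one degree of freedom per model (51 instead of 52 under the assumed coding; none for peak power). No new data and no change in procedures are needed.

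### Tukey's HSD, the only multiplicity correction named, does not fit a two-arm trial with three outcomes and no primary: depending on the reading, it leaves the outcomes uncorrected or costs power on the one contrast that matters

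*Protocol*

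**What the plan says.** The statistics paragraph (Protocol, Data Collection, Statistics and Sample-size Calculation) plans a repeated measures ANOVA for "differences on all variables of the repeated sprint test", "adjusting for age, sex, ethnicity, and peak power". Significance is set at 0.05, and Tukey's "HSD tests will be used to correct for multiple comparisons". No other multiplicity rule appears, and the paragraph does not say which means HSD is to compare.

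The rest of the design comes from other sections of the protocol:

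- **Purpose:** the aim is "to determine the effects of creatine supplementation on exercise performance at simulatedaltitude".
- **Preliminary testing:** "Outcomes measures are peak power (watts), relative peak power (watts per kilogram), and fatigue index (watts per second"). None is named primary. "The repeated sprint test involves six, 10-second sprints on a cycle ergometer".
- **Randomization and Supplementation:** allocation is made "using a double-blinded parallel design, to placebo (calcium 500 mg) or creatine supplementation (20 grams) for 2 days". It follows baseline testing and uses sex, age, ethnicity and peak power.
- **Baseline Testing and Simulated Altitude Testing:** the sprint test is done once before supplementation and once after it, under hypoxia. This gives 2 arms × 2 tests = 4 means per outcome.
- **Subjects:** sixty adults are to be enrolled. No allocation ratio is given.

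**The concern.** Tukey's HSD is built for all pairwise comparisons among several means of a single variable. Here there are only two arms, so the study question gives one between-arm comparison per outcome. The multiplicity that bears on the conclusion lies across the three outcomes, and HSD does not work there.

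The point is therefore not that detail is missing. The protocol names a particular method, and that method does not match the design. A later analysis plan that kept the sentence would keep the mismatch.

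What is at stake depends on how the sentence is carried out. Either a success on any one of three outcomes is more likely by chance than the stated 0.05 suggests, or the single contrast of interest pays for comparisons that do not answer the study question.

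**Working it through.** The protocol gives no derived figure to reproduce here: 0.05 is an input, and no power, SD or effect size accompanies the sixty participants.

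**Inputs from the protocol:** alpha 0.05 (taken as two-sided), 2 arms, 2 tests, 3 outcomes, 60 participants.

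**Assumptions:** 30 per arm, hence 58 error degrees of freedom, and the correlations between outcomes given below.

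**Per-comparison level of HSD.** Critical t = q/√2, where q is the 0.95 quantile of the studentized range for k means. The level is 2·P(T > t).

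| Means compared | q (df 58) | t | Level |
|---|---|---|---|
| k = 2 (the two arms) | 2.831 | 2.002 | 0.0500 |
| k = 4 (arm by test) | 3.741 | 2.645 | 0.0105 |

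Allowing for 4 to 8 covariate degrees of freedom (df 54 to 50) gives 0.0105 for k = 4 as well.

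**Reading (a): the arm or arm-by-test F test decides.** HSD does not enter that test, and on two means it equals the t-test (level 0.0500). Each outcome stays at 0.05.

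- Independent outcomes: 1 − 0.95³ = 0.143. This is unrealistic, since relative peak power is peak power per kilogram.
- Correlated outcomes, simulated t-tests with 30 per arm. Correlations are listed in the order peak–relative, peak–fatigue, relative–fatigue:

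| Assumed correlations | Chance of at least one false positive |
|---|---|
| 0.70, 0.40, 0.40 | 0.124 |
| 0.85, 0.60, 0.60 | 0.109 |
| 0.95, 0.80, 0.80 | 0.089 |

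The range is about 9–12%, roughly twice the stated 5%.

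**Reading (b): HSD over the four arm-by-test means decides, with an error term suited to each pair.** Four means give 4·3/2 = 6 pairs. Only one of them is creatine versus placebo at altitude.

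- Error for that contrast over three outcomes: 1 − (1 − 0.0105)³ = 0.031 if independent, and never more than 3 × 0.0105 = 0.0315. Error is controlled.
- Power: take the effect that gives 80% power at 0.05 with df 58 (back-solved, not from the protocol). By the noncentral t distribution, its power at critical t 2.645 is 58%. With df 54 or 50 it is also 58%.
- Sample size to recover 80% power (normal approximation): ((2.559 + 0.842)/(1.960 + 0.842))² = 1.47, or about 47% more participants. This ratio does not depend on the effect size or SD. For 90% power it is 1.40.

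**Sprint number as a further factor.** If the six sprints entered the model, there would be 2 × 2 × 6 = 24 means and 24·23/2 = 276 pairs within each outcome. None of these pairs lies across outcomes. This reading is less likely, because the listed outcomes read as whole-test summaries.

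**The case against.** The strongest reply is that this is an absence and not an error. The protocol never claims that HSD covers the three outcomes, and the family of means, the error term and a cross-outcome rule are commonly left to an analysis plan, which may exist. Under reading (a), moreover, HSD does no harm itself; the 9–12% comes from the untreated outcomes. Much of this stands: those omissions alone would be no finding, and the protocol states no rule that success on any one outcome suffices. What remains is that the protocol does choose a correction, and the one chosen cannot act where this design has its multiplicity.

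Two stronger readings are tempting and are not supported.

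- **Both harms at once.** A reader might infer that the plan leaves the outcomes inflated and also loses power. For the altitude contrast these exclude each other: if it is tested at 0.0105 per outcome, its error over three outcomes is at most about 3%.
- **Loss of error control under reading (b).** A reader might infer that HSD run with the within-subject mean square would badly inflate the between-arm contrast. Simulation gives 24% at an assumed residual correlation of 0.8, but only 2.1% at 0.2. The protocol specifies no error term and gives no correlation. A residual correlation of 0.8 is also implausible for peak power if baseline peak power is a covariate. The documents cannot carry this claim.

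It is also fair to say that the remedy does more than reword one sentence. That is acknowledged under the fix.

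**Conclusion.** The point holds as a mismatch between the named method and the design, and it should be fixed. Confidence is moderate, because the protocol does not say which means HSD compares, so the harm is conditional on the reading:

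- **(a)** About a 9–12% chance of at least one false positive over three outcomes. This rests on assumed correlations; the independent case is 14%.
- **(b)** Error is controlled, but power for the altitude contrast falls from 80% to about 58%. This rests on 30 per arm, four means and a suitable error term.

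These are alternatives and must not be added together.

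**What to change.** Replace the HSD sentence with wording along these lines:

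> For each outcome, the treatment effect is the creatine–placebo difference at the simulated-altitude test, adjusted for the baseline value of that outcome, age, sex, ethnicity and baseline peak power (entered once when peak power is the outcome). One outcome, named primary before unblinding, is tested at two-sided 0.05. Only if it is significant are the other two tested, by Holm's procedure (0.025, then 0.05). Tukey's HSD is used only for descriptive comparisons within an outcome.

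Which outcome is primary is the sponsor's choice. If the outcomes are not to be ranked, apply Holm across all three (0.0167, 0.025, 0.05). In the simulations, family error is 0.050 for the primary-first option and 0.032 to 0.049 for Holm across three.

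**Cost.** This changes the analysis model, from a repeated measures ANOVA to a baseline-adjusted comparison at altitude, and it changes the decision rule. It keeps the covariates already planned and leaves visits, measurements and sample size as they are.

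**Downside.** With a primary outcome, the other two face stricter thresholds and are not tested if the primary fails. Without ranking, a contrast with 80% power at 0.05 has about 65% at Holm's first step. Restoring 80% there would take ((2.394 + 0.842)/(1.960 + 0.842))² = 1.33 times the participants. That is a real loss against reading (a), though still above the 58% of reading (b).
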